3.6 Secondary endpoints

worsening and no change in functional assessment (ECOG, Karnofsky, Lansky) instead of the mean change in score from index date.

3.6 Secondary endpoints

- Added definition for improvement, worsening and no change in functional assessment for each scale (ECOG, Karnofsky, Lansky)
 - Modified the text related to secondary objective #7 and the text in Table 3-5 by reporting the percentage of patients reporting improvement, worsening or no change in work/school attendance instead of the percentage of patient that attend work/school/pre-school.
 - Clarified that the reason for change of work/school attendance will no longer be presented in a tabular format but listed instead.
 - Specified that the improvement, worsening or no change for performance status and work/school attendance will be reported at index date, baseline, 12, 24, 52 weeks windows and the "End of study".
 - Added definition of impact to complement the reporting of secondary objective #10
 - Data analysis of AEs: deleted the
-

time to first occurrence of CTC grade 2 for AESI;

- Data analysis of AESIs: deleted the duration of first event for CTC grade 2 or worse diarrhea (preferred term) and grade 2 or worse rash (preferred term).
- Corrected “ by treatment group” with “by age group”

- Updated list of variables with partially missing start and/or end dates that are imputed in Table 4-1 and Table 4-2 respectively.
- Added Table 4-3 to address imputation of partially missing start dates for variables for which an end date is not planned to be collected (e.g. death).

Section 4.3
Imputation rules

- Added a section to describe how partially missing dates are associated to pre-index or study period.

Added Section 4.3.1.1 Imputations and study periods (pre-index, on study)

- Added link to WHO website for growth chart.

Section 4.5

- Added references for the ECOG and Karnofsky scale correspondence, and for the Important Medical Event list.

Section 5 Reference

Table 3-4 Endpoints related to objective #6 30

Table 3-5 Endpoints related to objective #7 33

Table 3-6 Endpoints related to objective #8..... 34

Table 3-7 Clinically notable changes in vital signs 35

Table 3-8 List of all AESI grouping levels and related MedDRA terms 41

Table 4-1 Imputation of start dates (AE, Symptoms and complications, concomitant medications medical history, health resources utilization, non-drug treatment and other medical interventions)..... 44

Table 4-2 Imputation of end dates (AE, Symptoms and complications, concomitant medications, medical history, health resources utilization, non-drug treatment and other medical interventions)..... 45

Table 4-3 Imputation of start dates for assessments (Laboratory evaluation, vital signs, ECG, growth data, medical procedure (surgery), death, questionnaires, PROS disease history)..... 45

List of figures

Figure 1-1 Study design 16

List of abbreviations

BMI	Body mass index
BNP	Brain natriuretic peptide
CI	Confidence interval
CLOVES	Congenital lipomatous overgrowth, vascular malformations, epidermal nevi, scoliosis/skeletal and spinal syndrome
CRF	Case report/record form
CT	Computed tomography
CTCAE	Common Terminology Criteria for Adverse Events
ECG	Electrocardiogram
ECOG	Eastern Cooperative Oncology Group
eCRF	Electronic case report/record form
EDC	Electronic data capture
ER	Emergency room
FAO	Fibroadipose overgrowth
FDA	United States Food and Drug Administration
FIL	Facial infiltrating lipomatosis
HHML	Hemihyperplasia multiple lipomatosis syndrome
HRU	Healthcare resource use
IC50	Half maximal inhibitory concentration
ID	Identification
KTS	Klippel-Trenaunay syndrome
MAP	Managed access program
MCAP	Megalencephaly capillary malformation syndrome
MedDRA	Medical Dictionary for Regulatory Activities
MRI	Magnetic resonance imaging
N/A	Not applicable
NGS	Next-generation sequencing
PDS	Programming Datasets Specifications
PI3K	Phosphoinositide 3-kinases
PIK3CA	Phosphatidylinositol-3-kinase catalytic subunit alpha
PROS	PIK3CA-related overgrowth spectrum
SAP	Statistical analysis plan
SAS	Statistical Analysis System
SD	Standard deviation
SDS	Standard Deviation Scores

1 Introduction

This statistical analysis plan (SAP) describes all planned analyses for the Clinical Study Report (CSR) of study CBYL719F12002, a retrospective chart review study of patients with PIK3CA-Related Overgrowth Spectrum (PROS) who have received alpelisib as part of a compassionate use program. The content of this SAP is based on protocol CBYL719F12002 v1.0.

All decisions regarding final analysis, as defined in the present Statistical Analysis Plan (SAP) document, have been made prior to date of data abstraction.

1.1 Background and rationale

PROS describes a group of rare syndromes characterized by malformations and tissue overgrowth caused by somatic mutations in the PIK3CA gene.

The umbrella term PROS encompasses a group of syndromes with diverse phenotypes, including (but not limited to) CLOVES, MCAP, HHML, FAO, hemimegalencephaly, FIL, KTS, and others.

In PROS, individuals' malformations are seen as overgrowth in several different tissues such as skin, vasculature, bone, fat, and brain tissue depending on the specific disease. Some of the malformations are congenital malformations of the vasculature causing excessive immature vasculature tissue, which may or may not be associated with overgrowth of other tissue. PROS is characterized by a high degree of inter-individual phenotypic heterogeneity attributed to the location and extent of overgrowth and degree of vascular complications. The rate and timing of excess growth is also variable, sometimes limited to childhood, while other patients have progressive soft tissue overgrowth during adult life. These rare conditions have no approved medical treatment and are associated with a number of complications which depend on the anatomical site and extent of overgrowth and vascular malformations. These complications may include functional impairment (e.g., impairment in walking or activities of daily living), pain, recurrent superficial infections, thromboembolism, bleeding and/or organ dysfunction, all of which may be debilitating, and cause early morbidity and even mortality (Parker et al 2019). Current treatment includes surgical de-bulking procedures and amputation, and interventional procedures including sclerotherapy, laser and/or endovascular occlusive procedures. Regrowth following surgery occurs frequently and can require repeated surgery.

Sirolimus is an mTOR inhibitor that was introduced in 2011 as the first pharmacologic treatment for complicated vascular anomalies.

Sirolimus treatment has been shown to sequester components of mTORC2, which acts upstream on AKT signaling. However, it has not always been associated with lesion size reduction and has significant side effects, which include immunosuppression and hypertriglyceridemia (<https://lipidworld.biomedcentral.com/articles>).

Alpelisib is an oral α -specific class I PI3K inhibitor belonging to the 2-aminothiazole class of compounds. In biochemical assays, alpelisib potently inhibits the p110 α subunit of PI3K (IC₅₀ = 4.6 nM) \geq 50-fold compared to the other class I PI3K isoforms (e.g., p110 β IC₅₀ = 1156 nM, p110 δ IC₅₀ = 290 nM, p110 γ IC₅₀ = 250 nM), and it is inactive against most other kinases (Fritsch et al 2014). Alpelisib has demonstrated antitumor activity in a variety of cancer cell lines, particularly those harboring PIK3CA mutations and in xenograph models with mutated

or amplified PIK3CA (Keegan et al 2018) Clinical studies have also demonstrated the antitumor activity of alpelisib, especially in tumors with PIK3CA alterations, with a favorable safety profile (Juric et al 2019, Hoste et al 2018).

Venot et al (2018) described a postnatal mouse model of PROS/CLOVES that partially recapitulates the human disease. The model demonstrated the efficacy of alpelisib in preventing and improving organ dysfunction. The publication also describes how alpelisib was used in a compassionate use program to treat 19 patients (adult and pediatric) with PROS. This publication describes improvement in the disease symptoms in all patients receiving alpelisib treatment. Previously intractable vascular malformations became smaller, clinical complications such as congestive heart failure was improved, and hemihypertrophy and scoliosis was improved. As reported in the publication, the treatment was not associated with substantial adverse effects. This series of cases provides the first direct evidence supporting PIK3CA inhibition as a promising therapeutic option in patients with PROS. It should also be noted that the 19 patients described in this publication are also intended to be included in this study through medical charts into the study database.

Novartis is supporting compassionate use requests to allow treatment with alpelisib for patients with severe and/or life-threatening PROS as part of an overarching MAP. As of November 2019, this program has approved requests for the treatment of over 100 patients from 14 countries, of which so far 65 patients were expected to be treated with at least one dose of alpelisib at least 24 weeks prior to the planned cut-off date. Considering the meaningful number of patients that are being treated globally with alpelisib under compassionate use programs in this rare indication, this retrospective chart review will describe clinical and functional outcomes as well as safety in patients with PROS before treatment with alpelisib and at key time-points after treatment initiation.

1.2 Study objectives

Primary objective

To describe the efficacy of alpelisib as measured by the proportion of patients with response (yes/no) at Week 24 or 6 months (+/- 4 weeks), defined by achieving at least 20% reduction from index date in the sum of measurable target lesion volume (1 to 3 lesions, via central review of imaging scans), provided that none of the individual target lesions have $\geq 20\%$ increase from index date and in absence of progression of non-target lesions and without new lesions.

Secondary objectives

1. To assess changes in the sum of measurable target lesion (1 to 3 lesions) volume over time
2. To assess changes in the sum of all measurable (target and non-target) lesion volume over time
3. To assess changes in the sum of all measurable non-target lesion volume over time
4. To assess the duration of response defined as the time from first documented response, to the date of the first documented disease progression or death due to any cause.
5. To assess type of medication and non-drug therapies (e.g., concomitant PROS-related medications, PROS-related surgeries, duration of treatment/response) over time
6. To assess changes in PROS symptoms and complications (e.g., chronic bleeding/leaking, pain) over time
7. To assess changes in functional status (e.g., work/school/pre-school attendance, mobility) over time
8. To assess changes in HRU (e.g., ER visits, hospitalizations) over time
9. To assess changes in clinical assessments such as laboratory evaluation, vital signs and physical findings over time
10. To assess the safety and tolerability of alpelisib

1.3 Study design and settings

This study will be a site-based retrospective non-interventional medical chart review of pediatric and adult male and female patients with PROS.

Patients with PROS who have received at least one dose of alpelisib initiated at least 24 weeks before the cutoff date (09-Mar-2020) through a Novartis Managed access program (MAP) and satisfy the study inclusion criteria will be included in the study.

Patient-level data will be abstracted from medical charts of all eligible patients at all participating sites and will be pooled and assessed. Trained personnel at each site will abstract medical chart data. Informed consent will be obtained prior to data abstraction, as appropriate, for eligible patients interested in participating in the study where required.

[figure not shown]
The cut-off date of 09-Mar-2020 is selected to minimize the impact of the COVID-19 pandemic on the data integrity. Eligible patients who were initiated alpelisib on or before 23-Sep-2019 are expected to have 24 weeks of relevant assessments on or before 09-Mar-2020. At that time of the cut-off, COVID-19 pandemic did not have major consequences on the regular management of the patients in the countries participating in the MAP.

The **study period** will be defined as the period from the index date up to the cut-off date (09-Mar-2020) (Figure 1-1). During the study period all available data will be collected, if a patient has discontinued treatment prior to the cut-off date only data reported up to 30 days after the last date of study treatment will be abstracted and entered into the database.

The **index date (baseline)** will be defined as the date of alpelisib initiation. This date will be used as reference date for all assessments (safety and efficacy).

The **pre-index date** period will be defined as the period from up to 24 weeks prior to the index date (baseline) through to the day prior to the index date. (Figure 1-1).

Figure 1-1 Study design

Lesion assessments and definition

The volume of the target and all other measurable non-target lesion(s) will be assessed by a central imaging vendor and the details of this review will be captured in the Independent Central Review Charter. All available MRI scans, CT scans, and photographs will be shared with the vendor for assessment. Target lesions for the analysis of study endpoints will be independently selected by the central imaging reviewer using available images from up to 24 weeks prior to the index date, prior to any assessment of images from later in the study period. Central reviewers will take into consideration the clinical impact of the lesions.

Definition of target lesion

In the medical record, it is anticipated that measurable target lesions have already been selected by the treating physician based on the clinical/functional impact of such lesions. The clinical/functional impact will be associated with at least one of the following: patient's complaints, clinical symptoms, impaired organ function, functional limitations affecting patient's everyday life.

However, the target lesions will be independently selected by the central imaging reviewer using pre-index date scans and clinical information regarding symptoms provided by the investigator. More details can be found in the Central Imaging Site Manual.

In addition to the above, the target lesion may be:

- Anatomically reproducibly defined tissue(s) masses, composed of one or several tissue types
- Accurately measurable by imaging technique, MRI or other imaging modality
- Identified at index date and ideally its size would be at least 2 cm in longest diameter at the index date (for each selected lesion)

Target lesions will be determined by the local investigator and shared with the central reviewer using available images from index date prior to any assessment of images from later in the study period. If the central review team disagrees with the local investigator's target lesion selection, adjudication will occur.

Definition of non-target lesion

The non-target lesion consists of all other PROS-related anatomic lesions and may include the following:

- All anatomic lesions other than selected as target and may be measured at radiologic assessment (including small lesions less than 2 cm on MRI)
- Anatomic lesions, limb/truncal areas affected by PROS, organomegaly when they may be measured only by caliper/ruler (e.g., circumference of changed limb or body part)
- Truly non-measurable lesions (for example, superficial visual lesions, masses, organomegaly, PROS-related enlargement of anatomic area identified by physical exam that is not measurable by reproducible imaging technique)
- Definition of new lesion will be detailed in the in the Independent Central Review Charter.

2 Changes to the protocol specified analysis

The following update on time windows were implemented following outcome of internal audit conducted in early Jan 2021.

The time window was extended for the baseline imaging scans to include imaging scans performed up to 24 weeks prior to index date, instead of 12 weeks as indicated in the protocol, to allow for flexibility given the retrospective/real world nature of the EPIK-P1 study. The extension to the time window is intended to reflect the majority of the local medical practice and to include the maximum number of patients for the primary analysis. Furthermore, the extension to the time window is unlikely to modify the baseline assessment significantly as there is not published evidence that the disease may spontaneously improve.

The time window was extended for the 24 weeks scan to include imaging scan assessments between 20 weeks and 31 weeks for the primary endpoint as well as other endpoints, instead of 20 to 28 weeks as reported in the protocol. In accordance with clinical practice in the real world setting, some physicians conducted the imaging scan assessments at 6 months (corresponding to ~ 27 weeks). As such the time window was extended (24 weeks or 6 months +/-4 weeks) to estimate the 24 week endpoints efficiently.

3 Data analysis information

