The last interval, referred to as "end of study" in [Table 3-1](#), will include data available within the last 4 weeks prior to study treatment discontinuation plus 30 days or cut-off date, whichever comes first. When a patient discontinues data will be reported in the "end of study" time window as well as the one corresponding to the assessment (e.g., a patient discontinued treatment at week 58 data will be reported in the key point 52 weeks interval and in the "end of study").

In instances where more than one measure is reported in the time window associated with a key time-point (e.g., at 12 weeks), the measurement taken closest to the key-time point will be considered in the analysis. If two measures were taken on dates that are equidistant from the key time-point (e.g., 12 weeks - 5 days and 12 weeks + 5 days following the index date), the measure associated with a more severe condition (e.g., larger non-target lesion volume, higher pain severity score, lower functional assessment score) will be considered.

In instances where both a non-missing value and a missing or unknown value are reported in the time window associated with a key time-point, only the non-missing value will be considered in the analysis.

Similar rules applies to the volumetric measurement available for the patients.

If a patient has more than one volumetric measurement available for a single target lesion in the time window associated with the index date (i.e., up to 24 weeks prior to the index date) or at 24 weeks (i.e., ± 4 weeks) following the index date, the measurement taken closest to the index date or 24 weeks following the index date will be considered in the analysis. If two volumetric measurements for a single target lesion were taken on dates that are equidistant from the index date or 24 weeks following the index date, the larger of the two measurements (i.e., greatest volume) will be considered. All measurements available will be listed.

Imputation rules for the dates are reported in the [Appendix](#).

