3.5.1 Definition of response

Patients included in the analysis population for the primary endpoint will be defined as responders if they meet the following criterion:

- Patient achieved $\geq 20\%$ reduction from index date (or up to 24 weeks prior) in the sum of target lesion volumes (1 to 3 lesions, via central radiological assessment) by the change between the index date and 24 weeks or 6 months (+/- 4 weeks) following the index date
- None of the individual target lesions has $\geq 20\%$ increase from index date to Week 24 or 6 months (+/- 4 weeks)
- Patient did not permanently discontinue alpelisib prior to 24 weeks of treatment

- Patient did not require surgery as rescue therapy between index date and 24 weeks of treatment with alpelisib due to disease deterioration
- No progression of non-target lesions at Week 24 or 6 months (+/- 4 weeks)
- No appearance of new lesions at Week 24 or 6 months (+/- 4 weeks)

Patients will be defined as non-responders if they meet at least one of the following criteria:

- Patient achieved < 20% reduction from index date (or up to 24 weeks prior) in the sum of target lesion volumes (1 to 3 lesions, via central radiological assessment) by the change between the index date and 24 weeks or 6 months (+/- 4 weeks) following the index date
- Any of the individual target lesions has $\geq 20\%$ increase from index date to Week 24 or 6 months (+/- 4 weeks)
- Patient permanently discontinued alpelisib prior to 24 weeks of treatment
- Patient require surgery as rescue therapy between index date and 24 weeks of treatment with alpelisib due to disease deterioration.
- Progression of non-target lesions at week 24 or 6 months (+/- 4 weeks)
- Appearance of new lesion at week 24 or 6 months (+/- 4 weeks)
- Patients with MRI scan performed at week 24 or 6 months (+/- 4 weeks) for which the volumetric measurement of the selected target lesions (1 to 3 lesions, via central radiological assessment) cannot be calculated.

Patients will be considered as having a missing response if lesion volume(s) assessment at 24 weeks or 6 months (+/- 4 weeks) following the index date is not available and:

- Patient did not permanently discontinue alpelisib prior to 24 weeks of treatment and
- Patient did not require surgery as rescue therapy between index date and 24 weeks of treatment with alpelisib due to disease deterioration.

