3.5.3 Sensitivity and supportive/supplemental analyses

Supportive analyses reported in this section are targeted to investigate the robustness of the primary analysis, to model assumptions and data limitations using the efficacy population.

Sensitivity Analysis 1

Clinical practice, including frequency of monitoring patients with PROS is highly variable, and it is anticipated that imaging data may not be available at every key time point during the study period. Based on site feasibility discussions, the variability in frequency of imaging are due to the following reasons: individualized monitoring based on patient-specific needs or age; that

imaging may not be necessary/useful to monitor patient response; institution and insurance policies may not allow for frequent imaging.

Therefore a sensitivity analysis will be performed where missing volumetric assessments at week 24 will be multiply imputed for patients with missing response.

Multiple imputation (MI) is a simulation-based approach where missing values are replaced from the conditional distribution of missing data given the observed data and covariates, creating multiple completed data sets. These complete data sets can then be analyzed using standard methods and software for balanced data. Rubin (1987) presented rules how to combine the multiple sets of estimates to produce overall estimates and confidence intervals that adequately incorporate missing data uncertainty. Missing values for the change from index date in the sum of measurable target lesion volume will be imputed simultaneously based on an underlying joint normal distribution. The imputation model will include the longitudinal volumetric measurements (i.e. the MRI scans at index date and at other available time points), as well as covariates such as age, country and PROS lesion type. The number of imputations will be set to 100, the seed for the random function will be set to 45712002 (457<studycode>).

For each patient, the response status will be determined and for each imputed data set the proportion of patients with response will be calculated. The proportions of patients with response for each imputed data set will then be combined into an overall estimate using Rubin's rules (Little and Rubin 2002). The SAS procedures MI and MIANALYZE will be used to generate the multiple imputed data sets and to combine the results, respectively.

Sensitivity Analysis 2

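### SAP Amendment 3 openly widened both scan windows of the primary endpoint, but the readable SAP plans no response rate on the protocol windows, so the effect of the change is not shown

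*SAP*

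**What the plan says.** The protocol takes the baseline scan on the index date or in the 12 weeks before it (6.8.1, 6.9) and defines Week 24 as 20 to <28 weeks (Table 6-1). SAP Section 2 replaces both. A change made "following outcome of internal audit conducted in early Jan 2021" allows a baseline scan up to 24 weeks before index and extends Week 24 to "imaging scan assessments between 20 weeks and 31 weeks for the primary endpoint as well as other endpoints". SAP Table 3-1 puts the upper limit at <32 weeks. The version history dates this to Amendment 3, 19-Mar-2021.

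Section 2 gives its reasons. For baseline they are flexibility for retrospective data, agreement with most local practice, the wish "to include the maximum number of patients for the primary analysis", and the view that baseline would hardly change because no spontaneous improvement has been published. For Week 24 the reason is that some physicians scanned at 6 months, taken as about 27 weeks.

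The windows decide who is in the efficacy population (SAP 3.2), who has a missing response (3.5.1) and so who is a complete case (3.5). For each target lesion, SAP 3.3 uses the volume measured nearest to index or to week 24, and adds: "All measurements available will be listed". SAP 3.5.3 has two sensitivity analyses. In one, "missing volumetric assessments at week 24 will be multiply imputed for patients with missing response". In the other, missing responses are all counted as response, then all as non-response. SAP 3.5.2 adds reasons for missing response and a table of patients with and without the Week 24 assessment. Parts of the SAP are redacted, including entries in the Amendment 3 log.

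**The concern.** The response rate is the main efficacy result of a single-arm, descriptive study whose results are intended for health authorities (Protocol 9). Changing the scan windows can move both its numerator and its denominator. A reader of the planned summary tables would not see whether the rate depends on a change made in 2021. The listing might let someone reconstruct this by hand, but it gives no rate and no interval.

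Two smaller matters go with it. The upper limit of the Week 24 window is written in three ways. And SAP Section 1 says that all decisions on the final analysis preceded data abstraction, while Protocol 6.8 says that the SAP is final before data collection starts. Neither statement is squared with the 2021 change in SAP Section 2.

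**Working it through.** **1. Is there any planned summary on the protocol windows?** The readable primary-endpoint analyses are the complete-case estimate (SAP 3.5, 3.5.1), the with/without-assessment table (3.5.2), multiple imputation and best/worst case (3.5.3), and subgroups (3.5.4). All use the widened windows. Best/worst case is no substitute. A patient brought in by a later scan is no longer missing, and a patient with no scan in the 12 weeks before index was outside the protocol's efficacy population.

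**2. Do the stated reasons settle the effect?** With the SAP's month length (Appendix 4.1), 6 months = 6 × 30.4375 / 7 = 26.1 weeks; Section 2 says about 27. Both are below 28, so a scan done at 6 months was already inside the protocol window. The extension admits only scans at 28 weeks or later. The baseline argument concerns spontaneous improvement and is silent on growth before index. An older baseline in a growing lesion would work against response; longer treatment before the second scan could favour it. The direction is open.

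**3. How can the change act?** A scan at 20 to <28 weeks is at most 4 weeks from week 24; a scan at 28 to <32 weeks is at least 4 weeks away. A scan within 12 weeks of index is nearer than one at 12-24 weeks. So a lesion measured in both protocol windows keeps its volumes, except for a tie between scans at exactly 20 and 28 weeks, where the larger volume is used. What remains:
- Mainly, patients or lesions with no scan in one of the protocol windows are added. SAP 3.5.2 sums only paired lesions, so an extra scan can add a lesion to the sum.
- In fewer cases, target lesions are selected "using available images from up to 24 weeks prior to the index date" (SAP 1.3; 12 weeks in Protocol 6.5).
- Non-target or new-lesion findings may come from reads at 28-31 weeks.
- An MRI at 28-31 weeks "for which the volumetric measurement of the selected target lesions (1 to 3 lesions, via central radiological assessment) cannot be calculated" turns a missing response into non-response (SAP 3.5.1).

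One case is unclear. Suppose an MRI at week 22 is unmeasurable and a scan at week 29 is measurable. SAP 3.3 says that "only the non-missing value will be considered in the analysis", while SAP 3.5.1 makes a patient a non-responder on any one criterion. The documents do not say which rule prevails.

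**4. Window lengths.** Baseline goes from 12 to 24 weeks. Week 24 goes from 28 − 20 = 8 weeks to 32 − 20 = 12 weeks by Table 3-1. The longest possible gap between paired scans goes from under 12 + 28 = 40 weeks to under 24 + 32 = 56 weeks (16/40 = +40%). This describes the windows, not the response.

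**5. Illustration.** Clopper-Pearson limits are the 0.025 quantile of Beta(x, n − x + 1) and the 0.975 quantile of Beta(x + 1, n − x). For 15/50 this gives 0.179-0.446, width 0.267, as in Protocol Table 6-2. The n = 50 is the protocol's expected number of participants (6.6), not a count of complete cases. Assume that 15/50 respond on the SAP windows, that m of the 50 enter only through the widening, and that no other status changes. The protocol-window rate then runs from (15 − m)/(50 − m), if all m respond, to 15/(50 − m), if none do.

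| m (assumed) | all m respond | none of m responds |
|---|---|---|
| 3 | 12/47 = 25.5% (13.9-40.3) | 15/47 = 31.9% (19.1-47.1) |
| 5 | 10/45 = 22.2% (11.2-37.1) | 15/45 = 33.3% (20.0-49.0) |
| 10 | 5/40 = 12.5% (4.2-26.8) | 15/40 = 37.5% (22.7-54.2) |

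If 3 of 10 added patients respond, the rate is unchanged at 12/40 = 30.0% (16.6-46.5).

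**6. Upper limit.** Section 2 has 31 weeks, Table 3-1 has <32 weeks, and the volume-selection rule in 3.3 has 24 ± 4 weeks. The note under Table 3-1 suggests that the last is shorthand for 24 weeks or 6 months (27 + 4 = 31). Read literally, it excludes scans after week 28 that Table 3-1 includes.

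**The case against.** The change is disclosed and explained, the study is descriptive with no test, and wide windows suit a chart review without a common visit schedule. The closest-scan rule protects patients who were well measured in the protocol windows. Every measurement is to be listed. The number of patients affected may be small, and redacted text may contain the missing analysis. All of this stands. It limits the point to the readable SAP and makes the widening defensible, but it does not supply a rate on the protocol windows.

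Three stronger readings are tempting and are not supported:
- A reader might infer that the windows were widened with the responses in view. The documents give no dates of abstraction or central read and do not show that volumes or responses were known. The remark that some physicians scanned at 6 months suggests at most that scan timing was known. For the same reason the Section 1 sentence needs reconciling, but no actual breach is shown.
- A reader might infer that the change raises the rate. The direction is not determined.
- A reader might infer that many patients already counted change status. The closest-scan rule confines this to the exceptions above.

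**Conclusion.** The point holds as a request for one supplementary estimate. No readable planned summary shows whether the primary response rate depends on the 2021 window change, and the stated reasons cannot replace that estimate. The size is unknown because the documents do not give the number of patients who enter through the widening. The illustrated 22.2% to 33.3% around 30.0% rests on three assumptions: 50 complete cases, 5 patients added, and no other change in status. It is neither a bound nor a forecast. The three forms of the upper limit and the sentence on timing are minor matters of wording.

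**What to change.** (a) Unless a redacted section already contains it, add to SAP 3.5.3 a supplementary Clopper-Pearson estimate with baseline on the index date or up to 12 weeks before, and Week 24 = 20 to <28 weeks.
- Report any scans at exactly 28 weeks, since the protocol also writes ± 4 weeks.
- Keep the centrally selected target lesions and use only those with a baseline volume in the 12-week window.
- Take non-target and new-lesion status from central reads recorded for scans inside these windows. Where reads were not recorded per scan, keep the existing central conclusion and report how many patients this concerns.
- Report the numbers of patients and responders who enter through the wider baseline window, the wider Week 24 window or both, and the number whose status changes.
- State which rule prevails, 3.3 or 3.5.1, when the window holds both an unmeasurable MRI and a measurable scan.

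(b) Write one upper limit for Week 24 identically in Section 2, Table 3-1 and the volume-selection rule in 3.3.

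(c) Reconcile the Section 1 sentence with Section 2, and give the dates of abstraction and central read relative to 19-Mar-2021.

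The cost is SAP wording, one rerun of the primary table and one count table. Whether per-scan reads exist depends on the Independent Central Review Charter, which was not available; the fallback above avoids depending on it. The rerun has fewer patients and a wider interval, and it does not undo any effect of selecting lesions on scans 12-24 weeks before index.
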